## 2 Study Objectives

The objective of this study is to examine the impact of stopping ovulation/ovarian hormone stabilization, through the continuous administration of OCs for 3-months, on brain activation in response to reward and eating behaviors in women who binge eat ( $n=15$ ) using functional magnetic resonance imaging (fMRI). Participants will complete fMRI imaging and self-report questionnaires prior to OC administration and at the end of OC administration. We will examine within-subject changes that occur in these measures with OC administration.

Results will ultimately provide the pilot data necessary for larger mechanistic trials. We plan to accomplish the objective of this application by pursuing the following specific aims:

**Aim 1:** Quantify the effect of ovarian hormone stabilization on eating behaviors in women with binge eating.

**Aim 2:** Examine the effect of ovarian hormone stabilization on response to reward using fMRI and self-report questionnaires in women with binge eating.

### 3.1 General Design

This 16-week single-site study includes 4 primary visits, the hormone manipulation, and two check-in visits. The experimental protocol will last 3-months with a single follow-up assessment. Participants will undergo screening and consent (T0), a baseline assessment (T1), testing at the end of the experimental phase (T2), and a follow-up assessment one month post-intervention (T3). There will also be two check-in visits, approximately every 4-weeks during OC administration, to assess side effects and compliance. FMRI sessions will occur at T1 and T2. The study timeline is depicted in **Figure 2**, and the specific procedures that will take place are outlined in **Table 2** and detailed below in Section 6.

### 3.2 Outcome Variables

The primary endpoints for the Specific Aims are: 1) self-reported binge eating; 2) brain activation in dopamine-reward pathways, ROI include: nucleus accumbens, dorsal striatum, and DLPFC. Secondary end points include self-report measures of reward.

## 4 Subject Selection and Withdrawal

### 4.1 Inclusion Criteria

Participants will be women aged 18-34, normal weight, and engage in binge eating behaviors. Underweight individuals (BMI < 18.5) and overweight individuals (BMI > 31) will be excluded due to empirical reasons (i.e., the hypothesized mechanism may act differently in underweight EDs) and subject safety (e.g., increased risk of blood clots), respectively. Only participants capable of giving informed consent and understanding the risks associated with the study will be enrolled. Participants will be compensated upon completion of the study.

#### ***Inclusion Criteria.***

- 1) Current binge eating;
- 2) Age 18-34;
- 3) Regular menstrual cycle for at least 3-months;
- 5) Free of medication or medical illness that is contraindicated for use with the study medication;

### 4.2 Exclusion Criteria

Patients will not be permitted to enter this protocol if they meet any of the following. Notably, the individual factors that are associated with heightened risk for serious side effects from OCs are part of the exclusion criteria (i.e., smoker, 35+ years of age, hypertension, obesity, blood clotting disorder, liver/kidney/adrenal disease). The exclusion criteria used here are *much more conservative than used in the general practice of prescribing OCs*.

- any foreign metal objects or implants in your body as determined by the safety questionnaires (due to fMRI)
- use of birth control or hormones in the past 3-months
- hormonal contraceptives that are implanted (i.e. progestin IUD or implant)
- current pregnancy, lactation, or < 12-weeks postpartum
- previous serious, negative reaction to birth control
- current cigarette smoker
- < 18.5 BMI > 31
- history of bipolar disorder or psychotic episodes
- previous suicide attempt
- abnormal/undiagnosed vaginal bleeding; endometriosis
- recurrent migraine headaches or headaches with focal neurological symptoms
- hypertension or vascular disease (i.e., coronary artery disease, congestive heart failure, cerebrovascular disease)
- diabetes or other circulation problems
- blood clotting disorder

- porphyria
- breast, uterus/cervix, or vaginal cancer
- medical condition or medication use that increases serum potassium levels (including frequent laxative or diuretic use)
- high cholesterol
- history of VTE, DVT, PE, phlebonthrombosis, coronary thrombosis, thromboembolism, thrombophlebitis, or any type of blood clot or blood clot disorder (e.g., thromboembolic disease, Factor V Leiden), protein C or S deficiency, heart attack or stroke, atrial fibrillation, heart, liver, kidney, or adrenal disease, endocarditis, liver cancer, malignant melanoma, cholecystitis or pancreatitis, VTE or jaundice caused by pregnancy or birth control pills, recent significant period of immobility (e.g., pregnancy bed rest)
- Women determined to have any other symptoms, or any other potential contraindicated condition, that may impact their safety during the protocol will also be excluded from participation.

Pregnant women will be excluded from participation and women who become pregnant (although unlikely) will be withdrawn. Prior to enrollment, a pregnancy test will be completed. Heterosexual participants will be asked to use non-hormonal forms of birth control (e.g., barrier methods) to avoid pregnancy during this study. If a woman becomes pregnant during the study, participation will be discontinued.

## 4.3 Subject Recruitment and Screening

**Methods of recruiting for this study include:**

We will utilize recruitment methods that have been highly successful in the past including:

- 1) **Recruiting directly from the UNC Center of Excellence for Eating Disorders (CEED) outpatient treatment and research program:** CEED evaluates between 200-220 new patients per year and has an excellent track record of successful recruitment of women with EDs for research studies. Specifically, we will recruit women from the CEED via flyers, brochures, and direct recruitment by speaking with women who expressed interest in research on their referral form. In a recent clinical treatment trial for BN, 214 women contacted study staff and completed the phone screen and 80% were randomized.
- 2) **Established research registries at CEED and within the Department of Psychiatry at UNC:** CEED houses a research registry, which any member of the community (including current CEED patients) can join and consent to be contacted about future studies. There are currently 535 individuals signed up for the registry. CEED also has a registry of previous research study participants who consented to be re-contacted for future studies. Additionally, [name] has an established registry of individuals (3,000+) who previously completed online screening questionnaires for her hormone manipulation studies who agreed to be contacted for future studies.
- 3) **Targeted social media and website advertisements** (e.g., Facebook; ResearchMatch.org; Craigslist): In past studies, we have found social media to be an extremely effective strategy for recruitment at CEED.
- 4) **Flyers, brochures, and mass emails:** these will be disbursed in UNC Hospitals, across the university, across the larger community, and with established community partners who allow us to advertise and recruit for active studies (e.g., local medical offices). Mass emails will be sent monthly.

**5) Large-scale research registries:** UNC houses two large-scale research registries available to researchers: The Carolina Data Warehouse (CDW), a central data repository containing clinical, research, and administrative data sourced from the UNC Health Care System, and the website Join the Conquest. Within CDW currently, 557 female patients aged 18-35 have a diagnosis of BN within the medical record, with 151 of these diagnoses being made since 2017.

**6) NC TraCS Research Recruitment Service:** We will capitalize on the TraCS Research Recruitment Service's expertise in enrolling members of communities historically under-represented in research.

**Eligibility screening will include:**

- An initial phone or online screening that includes questions about past medical and mental health history to assess potential participants eligibility based on the criteria listed in sections 4.1 and 4.2.
- Participants will undergo a Clinical Screening Process to determine whether they are eligible to participate in this study.

## **4.4 Early Withdrawal of Subjects**

### **4.4.1 When and How to Withdraw Subjects**

Participants with significant clinical abnormalities will not be enrolled in the study or discontinued from the study.

Participant safety will be managed in several ways. First, risk is managed through study eligibility criteria. **The eligibility criteria used here are much more stringent than is used in general practice when prescribing OCs.** Once medication administration begins, subjects will complete weekly surveys that assesses the presence and intensity of symptomatology and side effects. This will include items related to mood, eating disorder symptoms, and OC side effects. The questionnaire will be completed online by subjects, and ratings will be transmitted to the study team in real-time. Members of the study team will receive immediate notification if a subject endorses active risk or severe adverse effects on the study form. Subjects will be contacted directly by [name] and an assessment will be conducted. If a subject does not complete the weekly form, a member of the study staff will contact them and conduct a safety assessment over the phone. Third, participants will complete a monthly visit to assess side effects and compliance. During monthly visits, mood symptoms will be monitored by administering the IDAS and eating disorder symptoms will be monitored with the EDEQ.

If a subject is deemed at elevated suicide risk at the enrollment appointment, they will not be enrolled in the study. If a subject is deemed at elevated suicide risk after study enrollment, they will be discontinued from the study protocol. Although we will not provide treatment or pay for treatment costs for subjects who are discontinued from the study, we will ensure subjects have appropriate treatment contacts and the risk is managed before terminating contact with the subject. For example, subjects deemed at emanate risk will be escorted to UNC Hospitals Emergency Department.

Any patient experiencing clinically significant and intolerable physical side effects will be discontinued. Any patient who is non-compliant with the medication will also be discontinued. This study will not provide treatment or pay for medical or psychological treatment costs for subjects. Patient's needing medical care will be referred to their primary care physician or provided appropriate referrals.

Should an AE occur, we will comply with reporting requirements for adverse events. As Principal Investigator, [name] will be responsible for the documentation, investigation, and follow-up of all study-related AE. All AE will be reported according to IRB guidelines. All moderate or severe AE will be reported to the UNC IRB within 7 days.

Because this is an open label study with no blinding and [name] has direct access to all data collected, PI [name] will primarily oversee subject safety, in collaboration with study co-investigators, and make the determination of when to withdraw subjects.

## 5 Study Drug

### 5.1 Description

Drug	Dosage	Formulation
Drospirenone Ethinyl-Estradiol 3/0.03mg (oral contraceptive)  Drospirenone Active ingredient: synthetic progestin Chemical name: 1,2-dihydrospiorenone  Ethinyl-Estradiol Active ingredient: Ethinyl Estradiol Chemical name: 17-ethinyl-3, 17-estradiol	3/0.03 mg daily	Oral tablet

### 5.2 Treatment Regimen

Participants complete a 84-day regimen of Drospirenone .30mg Ethinyl-Estradiol .03mcg. Subjects will begin OC administration on the first day of their period after the T1 visit. OCs will be taken continuously for 84 days.

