## 1.2 Investigational Agent

### Drospirenone/Ethynodiol-Diol (3mg; 30mcg)

#### Description

Drospirenone/Ethynodiol-Diol is a low-dose monophasic contraceptive tablet for oral administration containing 3mg of drospirenone and 30mcg of ethynodiol-diol. Drospirenone is a synthetic progestin chemically described as 1,2-dihydrospirorenone. Drospirenone is a spironolactone analogue with antimineralcorticoid activity. Preclinical studies in animals and *in vitro* have shown that drospirenone has no androgenic, estrogenic, glucocorticoid, or antiglucocorticoid activity, and exhibits antiandrogenic activity. The two main metabolites of drospirenone found in human plasma were shown to not be pharmacologically active. In *in vitro* studies with human liver microsomes, drospirenone was metabolized only to a minor extent mainly by cytochrome P450 3A4. Ethynodiol-diol is a syntenic estrogen chemically described as 19-nor-17 $\alpha$ -pregna 1,3,5(10)-triene-20-yne-3, 17-diol.

The medication is provided with 21-active pills and 7-inactive (placebo) pills. The inactive pills are taken to induce bleeding (though not technically a menses because ovulation did not occur) and are hormone free. The inactive pills will not be used in this study.

**Figure 1.** Structural formula for Drosiprenone/Ethinyl-Estradiol

Inactive Ingredients: lactose monohydrate NF, corn starch NF, magnesium stearate NF, hypromellose USP, talc USP, titanium dioxide USP, ferric oxide pigment, red NF.

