#### Pharmacology

OCs decrease the risk of becoming pregnant by suppressing ovulation.

Drosiprenone is a synthetic progestin that is an analog to spironolactone. Drosiprenone differs from other synthetic progestins in that its pharmacological profile in preclinical studies shows it to be closer to endogenous P4. As such it has anti-mineralocorticoid properties and is not androgenic. Preclinical studies show that drosiprenone is an antiandrogenic. Ethinyl-estradiol is a semisynthetic alkylated estradiol with a 17-alpha-ethinyl substitution. It has high estrogenic potency when administered orally.

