#### **Summary of Previous Human Experience**

One study to date has used the proposed OC in a BN population and observed a beneficial effect of use on BN symptoms for some women. No severe adverse events or outcomes were mentioned in the published report.

Drosiprenone/Ethinyl-Estradiol is FDA-approved as an oral contraceptive and for the treatment of PMDD. It is effective in reducing the risk for pregnancy and for treating PMDD through its suppression of ovulation.

Drosiprenone/Ethinyl-Estradiol has been widely researched including in psychiatric populations (i.e., PMDD) and healthy populations, including application in a BN population.

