## 1.5 Dose Rationale and Risks/Benefits

### Dose Rationale

The dose of OC chosen is an FDA-approved dosage. Further, this specific OC and dose have shown sensitivity to BN symptom change previously. Thus, the drug protocol, route of administration, dosage, dosage regimen, and dosage period, mirrors FDA-approval for this drug and previous research studies using this drug in an ED population. We are not conducting this study to support a new indication, dose, or route of administration for

clinical use. Previous studies have also implemented Drospirenone/Ethinyl-Estradiol continuously and were deemed IND exempt (PI [name]). Subjects in this proposal will take oral contraceptive birth control of 84 continuous days. This represents an ‘off label’ use as the pill packs come with 7 days of inactive pills to induce bleeding. However, as described below, this ‘off label’ practice does not increase participant risk and frequently occurs as part of standard clinical practice.

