low mood). Thus, it is very likely some of the reported side effects are due to the participant's expectations regarding publicized OC side effects.

In this proposal, subjects will take the OCs continuously. Drospirenone/Ethinyl-Estradiol 3/.03mg is provided in a 21/7 regimen that includes a hormone free interval of inactive pills. The continuous use of Drospirenone/Ethinyl-Estradiol by [name] did not require an IND application to be submitted. Regardless, OCs have been prescribed 'off label' by physicians to be taken in a continuous fashion for decades. In one survey, 70% of providers reported prescribing cyclic OCs in a continuous manner. The advent of OCs marketed for continuous cycle use are not new concepts. Continuous cycle use was first studied in the 1960's and, as stated, cyclic OCs are frequently prescribed to be taken continuously in order to treat menstrual disorders such as menorrhagia, dysmenorrhea, endometriosis, PMS, PMDD, and for convenience. The introduction of continuous cycle OCs allowed for OCs taken continuously to be covered by insurance: the challenge with 'off label' continuous use of OCs is that some insurance companies will not cover the extra pill packs required due to the placebo pills being skipped. Otherwise there is no difference between OCs marketed for continuous use vs. for cyclic use.

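### Section 5.2 states drug amounts that differ from the study-drug table in section 5.1 by 10-fold for drospirenone and 1000-fold for ethinyl-estradiol

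*Combined protocol and SAP*

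**What the plan says.** All references are to the combined protocol and SAP.

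- **Section 5.2, Treatment Regimen:** "Participants complete a 84-day regimen of Drospirenone .30mg Ethinyl-Estradiol .03mcg".
- **Section 5.1, Description (study-drug table):** the dosage column reads "3/0.03 mg daily", and the product name in the same table carries the same 3/0.03 mg strength.
- **Section 1.2, Description:** a tablet "containing 3mg of drospirenone and 30mcg of ethynodiol-diol". The heading repeats 3 mg and 30 mcg.
- **Section 1.5, Risks/Benefits:** "Drospirenone/Ethinyl-Estradiol 3/.03mg is provided in a 21/7 regimen that includes a hormone free interval of inactive pills".
- **Section 1.5, Dose Rationale:** the choice of dose is defended on the ground that "this specific OC and dose have shown sensitivity to BN symptom change previously".
- **Study Summary, Dose:** a single figure of 3.03 mg, not split by component.

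The name of the estrogen also varies within section 1.2. The heading and Description text call it ethynodiol-diol. The Figure 1 caption reads "Structural formula for Drosiprenone/Ethinyl-Estradiol", the Pharmacology text says "Ethinyl-estradiol is a semisynthetic alkylated estradiol with a 17-alpha-ethinyl substitution", and the summary of human experience says "Drosiprenone/Ethinyl-Estradiol is FDA-approved as an oral contraceptive and for the treatment of PMDD".

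**The concern.** Sections 5.1 and 5.2 are both operative text about the same product, and they cannot both be followed. Section 5.2 is where a pharmacist, monitor, IRB member or replicating team would look to see what participants take. While the two sections disagree, adherence to the protocol dose cannot be verified cleanly, and a dose rationale built on one specific dose is ambiguous.

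The text was still in force when enrollment closed: the 1/6/2022 entry under Protocol Updates says that remaining participants would complete the study. The study is also meant to inform a larger trial and to be published (sections 2 and 10), so the discrepancy could carry forward into either.

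**Working it through.** **Inputs**

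| Source | Drospirenone | Estrogen component |
|---|---|---|
| Section 5.2 | .30 mg | .03 mcg |
| Section 5.1 table | 3 mg | 0.03 mg |
| Section 1.2 heading and text | 3 mg | 30 mcg |
| Section 1.5, Risks/Benefits | 3 mg | .03 mg |

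**Step 1. Common units (1 mg = 1000 mcg).** 0.03 mg = 30 mcg, so sections 5.1, 1.2 and 1.5 agree on amounts. Section 5.2 is the only place that gives .30 mg and .03 mcg.

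**Step 2. Size of the gap, section 5.1 over section 5.2.**
- Drospirenone: 3 / .30 = 10.
- Ethinyl-estradiol: 30 mcg / .03 mcg = 1000.

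**Step 3. Could a different number or fraction of tablets explain it?** Changing the tablet count scales both components equally and leaves their ratio fixed.
- Section 5.1: 3 mg / 0.03 mg = 100, i.e. 100:1.
- Section 5.2: .30 mg = 300 mcg, and 300 / .03 = 10,000, i.e. 10,000:1.

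The ratios differ by 10,000 / 100 = 100, so no multiple or fraction of one product gives the other.

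**Step 4. Could section 5.2 be an 84-day total rather than a daily amount?** At the section 5.1 amounts, 84 days come to 84 × 3 = 252 mg of drospirenone and 84 × 30 = 2,520 mcg of ethinyl-estradiol. The section 5.2 figures are below even one day's amount in section 5.1, so this reading fails.

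**Step 5. The Study Summary figure.** 3 + 0.03 = 3.03, so 3.03 mg is the sum of the section 5.1 amounts. The section 5.2 amounts would sum to 0.30 + 0.00003 = 0.30003 mg. The Study Summary is therefore not a third dose; it only fails to give a strength per component.

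**Step 6. Does anything explain the difference?** None of the Protocol Updates entries concerns dose, section 5.2 is current body text, and both statements are complete, so neither supersession nor redaction accounts for it.

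**Step 7. Effect on the statistics.** The sample size rationale in section 7.1 and the methods in section 7.2 do not use the dose.

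**The case against.** The strongest counter-argument is that this is a drafting slip with little practical effect. Section 5.2 stands alone against sections 5.1, 1.2 and 1.5. Section 1.2 describes one fixed monophasic tablet, and sections 5.7 and 5.9 route supply through the institution's pharmacy storeroom and Investigational Drug Service. No section describes compounding, tablet splitting or a second product. The ratio argument itself shows that the tablet described could not deliver the section 5.2 amounts. Enrollment has closed, so no new participant can be dosed from this text. Strictly, too, this is an internal inconsistency rather than a miscalculation.

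Much of that stands, and it is why no misdosing is alleged. It does not reconcile the two sections, and closed enrollment leaves open which product and strength those already treated received.

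A second argument is that the text was machine-read from PDF and the drug wording is visibly unstable, with variant spellings of drospirenone and the ethynodiol-diol wording in section 1.2. For section 5.2 a reading error is unlikely, because it would have to alter both the drospirenone number and the ethinyl-estradiol unit in one sentence. If the decimal in .30 were misplaced, the 1000-fold conflict in the estrogen would remain. Checking that sentence on the source page is nevertheless reasonable and costs nothing.

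The argument carries more weight for the side items. The 3.03 mg figure could be 3/.03 mg with the slash lost, in a table that is plainly broken. The ethynodiol-diol wording is confined to section 1.2, which itself uses ethinyl-estradiol elsewhere. Both are lower-confidence points, and the main finding depends on neither.

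**Conclusion.** The concern holds, with high confidence. Sections 5.1 and 5.2 disagree 10-fold on drospirenone and 1000-fold on ethinyl-estradiol, and their component ratios differ 100-fold, so they describe different strengths rather than different tablet counts. The conclusion assumes only that the amounts in both sections were transcribed correctly.

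This must be corrected because it concerns the identity and amount of the only intervention. Sample size, power and analysis are unaffected. The estrogen's name in section 1.2 and the combined figure in the Study Summary are minor consistency points to settle at the same time. No view is taken on which statement is right.

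**What to change.** 1. Reconcile the Study Summary and sections 1.2, 5.1 and 5.2 so that one product name, and one strength with its unit for each component, appears everywhere.
2. Check the section 5.2 sentence and the estrogen's name in section 1.2 against the source page.
3. Confirm from the dispensing record and the drug reconciliation form required by section 5.9.4 which product and strength were supplied.
4. Notify the IRB of the correction.

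The cost is a short text correction, a check of existing records and one IRB notification. Sample size, data collection and analysis do not change.
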